### 3 Trial objectives, estimands, and endpoints

Trial objectives and endpoints are presented in [Panel 3](#).

An estimand framework is used to ensure that occurrence of intercurrent events is taken into account. Further details about the estimands and statistical analyses of the endpoints are presented in [Panel 4](#) and in Section 11.

#### Panel 3: Objectives and endpoints

Objectives	Endpoints

Primary objective
 
To compare the efficacy of 4 different dose regimens of LEO 138559 with placebo in subjects with moderate-to-severe AD.
	
Primary endpoint
 
 
Percent change in EASI score from baseline to Week 16.
 
 
Exploratory endpoints (efficacy)
 
 
Achievement of EASI-50 at Week 16.
 
Achievement of EASI-75 at Week 16.
 
Achievement of EASI-90 at Week 16.
 
Achievement of EASI-100 at Week 16.
 
Change in EASI score from baseline to Week 16.
 
Change in SCORAD score from baseline to Week 16.
 
Percent change in SCORAD score from baseline to Week 16.
 
Achievement of vIGA-AD score of 0 (clear) or 1 (almost clear) at Week 16.
 
Change in BSA from baseline to Week 16.
 
Percent change in BSA from baseline to Week 16.
 
 
Exploratory endpoints (PROs)
 
 
Reduction of ADSD Worst █ score (weekly average) <math>\geq 4</math> from baseline to Week 16.
 
Change in DLQI (and individual domain scores) from baseline to Week 16.
 
Percent change in DLQI (and individual domain scores) from baseline to Week 16.
 
Change in POEM score (and individual item scores related to itch and sleep) from baseline to Week 16.
 
Percent change in POEM score from baseline to Week 16.
 
Change in EQ-5D-5L index score from baseline to Week 16.
 
Percent change in EQ-5D-5L index score from baseline to Week 16.
 

THIS DOCUMENT CONTAINS CONFIDENTIAL INFORMATION AND MUST NOT BE COPIED OR MADE AVAILABLE TO ANY THIRD PARTY WITHOUT THE PRIOR WRITTEN CONSENT OF THE LEO PHARMA GROUP

Objectives	Endpoints
	
 
Change in EQ-5D-5L VAS score from baseline to Week 16.
 
Percent change in EQ-5D-5L VAS score from baseline to Week 16.
 
Change in HADS score from baseline to Week 16.
 
Percent change in HADS score from baseline to Week 16.
 
Change in Difficulty [REDACTED] (weekly average) from baseline to Week 16.
 
Percent change in Difficulty [REDACTED] (weekly average) from baseline to Week 16.
 
Change in Nocturnal [REDACTED] (weekly average) from baseline to Week 16.
 
Percent change in Nocturnal [REDACTED] (weekly average) from baseline to Week 16.
 
Change in Frequency of [REDACTED] During the Night (weekly average) from baseline to Week 16.
 
Percent change in Frequency of [REDACTED] During the Night (weekly average) from baseline to Week 16.
 
Change in WPAI-SHP domain scores from baseline to Week 16.
 
Percent change in WPAI-SHP domain scores from baseline to Week 16.
 
Change in SCORAD Part C (Pruritus VAS) score from baseline to Week 16.
 
Percent change in SCORAD Part C (Pruritus VAS) score from baseline to Week 16.
 

Secondary objective	
To compare the safety of 4 different dose regimens of LEO 138559 with placebo in subjects with moderate-to-severe AD.	
Secondary endpoint
 
 
Number of TEAEs recorded for each subject from baseline to Week 16.
 
 
Exploratory endpoint (safety)
 
 
Time from baseline to use of any rescue treatment.
 
Number of TEAEs recorded for each subject from baseline to Week 32.
 
Number of TEAEs recorded for each subject from Week 16 to Week 32.
 
Having a positive ADA response from baseline to Week 32.
 

Exploratory objectives	
To compare the efficacy of 4 different dose regimens of LEO 138559 with	Exploratory endpoint (PRO)

THIS DOCUMENT CONTAINS CONFIDENTIAL INFORMATION AND MUST NOT BE COPIED OR MADE AVAILABLE TO ANY THIRD PARTY WITHOUT THE PRIOR WRITTEN CONSENT OF THE LEO PHARMA GROUP

Objectives	Endpoints
placebo in subjects with moderate-to-severe AD, having a weekly average ADSD Worst [REDACTED] score of $\geq 4$ at baseline.	
 
Reduction of ADSD Worst [REDACTED] score (weekly average) <math>\geq 4</math> from baseline to Week 16.
 

To compare the efficacy of 4 different dose regimens of LEO 138559 with placebo in subjects with moderate-to-severe AD, having a DLQI score of $\geq 4$ at baseline.	
Exploratory endpoint (PRO)
 
 
Reduction of DLQI <math>\geq 4</math> from baseline to Week 16.
 

To compare the efficacy of 4 different dose regimens of LEO 138559 with placebo in subjects with moderate-to-severe AD, having a POEM score of $\geq 4$ at baseline.	
Exploratory endpoint (PRO)
 
 
Reduction of POEM <math>\geq 4</math> from baseline to Week 16.
 

To evaluate the PK of LEO 138559 in subjects with moderate-to-severe AD.	
Exploratory endpoint (PK)
 
 
Serum concentration of LEO 138559 at Weeks 1, 2, 4, 8, 12, 16, 20, and 32.
 

To evaluate the effect of treatment with LEO 138559 compared with placebo for 16 weeks on biomarkers in subjects with moderate-to-severe AD.	
Exploratory endpoints (PD)
 
 
Change in expression of biomarkers in serum from baseline to Week 2, Week 4, and to Week 16, respectively.
 
Change in skin Staphylococcus aureus abundance and microbiome profile from baseline to Week 16.
 
Change in skin lipid and molecular profile from baseline to Week 4, and to Week 16, respectively.
 
Change in biomarker expression from baseline to Week 16 in lesional skin biopsies.
 

**Abbreviations:** AD = atopic dermatitis; ADA = anti-drug antibodies; ADSD = Atopic Dermatitis Symptom Diary; BSA = body surface area; DLQI = Dermatology Life Quality Index; EASI = Eczema Area and Severity Index; EASI-50 = at least 50% reduction in EASI score; EASI-75 = at least 75% reduction in EASI score; EASI-90 = at least 90% reduction in EASI score; EASI-100 = 100% reduction in EASI score; EQ-5D-5L = EuroQoL 5 Dimension Health Questionnaire 5 Level; HADS = Hospital Anxiety and Depression Scale; PK = pharmacokinetics, PD = pharmacodynamics; POEM = Patient-Oriented Eczema Measure; PRO = patient reported outcome; SCORAD = SCORing Atopic Dermatitis; TEAEs = treatment-emergent adverse events; VAS = Visual Analogue Scale; vIGA-AD = validated Investigator Global Assessment Scale for Atopic Dermatitis; WPAI-SHP = Work Productivity and Activity Impairment: Specific Health Problem.

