#### 11.3.7.2 Estimands for binary endpoints

The primary estimand for binary endpoints attempts to quantify the effect of treatment in the hypothetical scenario where:

- All subjects remain on treatment except for those permanently discontinuing IMP due to lack of efficacy or the occurrence of an AE related to worsening of AD. AEs considered related to worsening of AD will be specified in the SAP.

The occurrence of the following intercurrent events will be treated as indicating a failure of the randomized treatment:

THIS DOCUMENT CONTAINS CONFIDENTIAL INFORMATION AND MUST NOT BE COPIED OR MADE AVAILABLE TO ANY THIRD PARTY WITHOUT THE PRIOR WRITTEN CONSENT OF THE LEO PHARMA GROUP

- Permanent discontinuation of IMP due to lack of efficacy or the occurrence of an AE related to worsening of AD.
- Initiation of rescue treatment.

The estimand is described by the following attributes:

- A. Target Population: Subjects with moderate-to-severe AD, as defined through the inclusion and exclusion criteria listed in Section 5.
- B. Variable: Applied to binary endpoints.
- C. Treatment conditions: LEO 138559 dose regimens 1-4 versus placebo.
- D. Strategies for handling intercurrent events
  - a. Subjects initiating rescue treatment or permanently discontinuing IMP due to lack of efficacy or the occurrence of an AE related to worsening of AD are defined as treatment failures according to the composite strategy.
  - b. For subjects permanently discontinuing IMP due to reasons other than lack of efficacy or the occurrence of an AE related to worsening of AD, the hypothetical strategy will be used to estimate the effect of treatment in the hypothetical scenario where subjects do not permanently discontinue IMP for reasons other than lack of efficacy or the occurrence of an AE related to worsening of AD.
- E. Population level summary: Difference in response rates between the treatment conditions.

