##### TEAEs

An event will be considered treatment-emergent if started after the first dose of IMP or if started before the first dose of IMP and worsened in severity after first dose of IMP. An event will not be considered treatment-emergent if starting 18 weeks after the last dose of IMP. The tabulations described in the following will only include the TEAEs. All AEs recorded during the course of the trial will be included in subject data listings.

AEs will be summarized in terms of the number of subjects with at least 1 event, the percentage of subjects with at least 1 event, the number of events, and the event rate per 100 patient years of observation time.

Related AEs are defined as AEs for which the investigator has not described the causal relationship to IMP as 'not related'. The number of related AEs and the number of subjects with each type of related AE will be tabulated.

THIS DOCUMENT CONTAINS CONFIDENTIAL INFORMATION AND MUST NOT BE COPIED OR MADE AVAILABLE TO ANY THIRD PARTY WITHOUT THE PRIOR WRITTEN CONSENT OF THE LEO PHARMA GROUP

An overall summary of the number of events and the number (percentage) of subjects with any TEAEs, deaths, SAEs, AESIs, permanent discontinuations from IMP and/ or withdrawals from the trial due to AEs, treatment-related AEs, and severe AEs will be presented.

Tabulations by SOC and PT will be presented for all AEs, SAEs, related AEs, AESIs, and AEs leading to withdrawal from trial and/or permanent discontinuation of IMP. In addition, all AEs will be presented by severity and causal relationship to IMP, respectively.

SAEs will be evaluated separately, and a narrative will be given.

AEs leading to withdrawal from trial or permanent discontinuation of IMP will be tabulated and listed. No narratives will be given.

Other events (medication error) will be listed. No narratives will be given.

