### 12.2.4 Recording and follow-up of AEs

#### AE recording

When an AE occurs, it is the responsibility of the investigator to review all documentation (e.g. hospital progress notes, laboratory, and diagnostics reports) related to the event.

AEs reported by the subject or observed by the investigator must be recorded on the AE form of the eCRF and should be described in the following manner:

The AE term must be in precise English medical terminology (that is, not necessarily the exact words used by the subject). Whenever possible, a specific diagnosis should be stated (e.g. 'allergic contact dermatitis').

Any clinically significant aggravation/exacerbation/worsening of any medical condition(s) (including the trial disease), compared to screening, must be reported as an AE.

THIS DOCUMENT CONTAINS CONFIDENTIAL INFORMATION AND MUST NOT BE COPIED OR MADE AVAILABLE TO ANY THIRD PARTY WITHOUT THE PRIOR WRITTEN CONSENT OF THE LEO PHARMA GROUP

AD is a fluctuating disease with possible periods of remission. In case of relapses/recurrences, only aggravations/exacerbations exceeding normal disease fluctuation or lesions appearing in a body area normally not affected by AD should be reported as an AE.

The duration of the AE must be reported by the start date and stop date of the event unless the event is ongoing. If the event is ongoing, it will be marked as ongoing. In addition, it will be recorded whether the AE started on the same day as IMP was administered and if so, whether before or after IMP dosing.

AEs must be classified in terms of severity, causality, and outcome according to the definitions below.

Action taken with IMP: any action taken with IMP as a consequence of the AE must be recorded in the eCRF (dose not changed, drug interrupted, drug discontinued, not applicable, unknown).

For subjects participating in the qualitative interview, AEs reported during the interview may be reported retrospectively.

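### The secondary safety endpoint counts reportable worsening of AD as a TEAE and no summary without it is planned, so the headline comparison with placebo can dilute an excess of other events

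*Combined protocol and SAP*

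**What the plan says.** Four places in the protocol matter here.

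- **Endpoint.** Section 3, Panel 3 gives one secondary endpoint, "Number of TEAEs recorded for each subject from baseline to Week 16". It serves the objective of comparing the safety of each regimen with placebo.
- **What is recorded.** Section 12.2.4 (AE recording) states: "Any clinically significant aggravation/exacerbation/worsening of any medical condition(s) (including the trial disease), compared to screening, must be reported as an AE". For relapses of AD it narrows this to "only aggravations/exacerbations exceeding normal disease fluctuation or lesions appearing in a body area normally not affected by AD".
- **What is tabulated.** Section 11.3.13.1 defines treatment emergence by timing alone: "An event will be considered treatment-emergent if started after the first dose of IMP", or if an earlier event worsens afterwards. Then "The tabulations described in the following will only include the TEAEs". The overall summary covers any TEAE, deaths, SAEs, AESIs, discontinuations due to AEs, related AEs and severe AEs. Events are also broken down: "Tabulations by SOC and PT will be presented for all AEs, SAEs, related AEs, AESIs, and AEs leading to withdrawal from trial" and/or discontinuation of IMP.
- **A term list exists in principle.** Section 11.3.7.2 says "AEs considered related to worsening of AD will be specified in the SAP". That list serves the efficacy estimands in Section 11.3.8. Section 11.3.13 does not use it, and no TEAE summary without those terms is described.

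**The concern.** In a trial of an AD drug against placebo, a reportable flare is largely a sign that the treatment is not working. When it enters the safety count, an arm with poor efficacy collects extra TEAEs, and that arm is the reference for every safety comparison. An active regimen with more infections, injection-site reactions or other events could then show a total close to that of placebo.

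The design makes such an imbalance plausible. Topical AD treatment stops at Week -1 (Section 4.1) and stays prohibited except as rescue (Sections 6.5 and 6.7). Section 2.5 warns that the condition may worsen when AD treatment is changed. Worsening is judged against screening, which precedes the washout. The degree of masking would also vary with the efficacy of the regimen, which matters when doses are being compared.

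**Working it through.** **Is there a figure to reproduce?** No. The documents state no TEAE rate, AD-worsening rate or power for this endpoint. The steps below show what the definitions imply, followed by an illustration on assumed rates.

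**Step 1: the definitions.** Section 12.2.4 puts reportable AD worsening into the AE data. Section 11.3.13.1 filters by timing only. AD worsening that starts after the first dose is therefore a TEAE and enters the per-subject count and the overall summary.

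**Step 2: the direction.** Let *b* be non-AD TEAEs per placebo subject, *e* the true non-AD excess on an active regimen, and *w_P* and *w_A* the AD-worsening TEAEs per subject on placebo and active.

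- Observed difference = (b + e + w_A) − (b + w_P) = e − (w_P − w_A)
- Observed ratio = (b + e + w_A) / (b + w_P)
- Non-AD ratio = (b + e) / b

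The difference is understated exactly when w_P exceeds w_A.

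**Step 3: illustration.** All rates are assumptions.

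| b | e | w_P, w_A | Observed ratio | Observed difference | Non-AD ratio |
|---|---|---|---|---|---|
| 0.8 | 0.4 | 0.10, 0.05 | 1.25/0.90 = 1.39 | 0.35 | 1.50 |
| 0.8 | 0.4 | 0.20, 0.05 | 1.25/1.00 = 1.25 | 0.25 | 1.50 |
| 0.8 | 0.4 | 0.40, 0.10 | 1.30/1.20 = 1.08 | 0.10 | 1.50 |
| 0.8 | 0.2 | 0.40, 0.10 | 1.10/1.20 = 0.92 | −0.10 | 1.25 |
| 1.2 | 0.4 | 0.10, 0.05 | 1.65/1.30 = 1.27 | 0.35 | 1.33 |
| 1.2 | 0.4 | 0.40, 0.10 | 1.70/1.60 = 1.06 | 0.10 | 1.33 |

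The effect runs from slight dilution to a reversed sign. Which row applies cannot be settled from the documents.

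**Step 4: which regimens.** Section 11.1 assumes that 20%, 20%, 30% and 40% of subjects on regimens 1 to 4, and 40% on placebo, withdraw or have an intercurrent event by Week 16. This is not an AD-worsening rate. As a rough guide to disease control, though, it separates regimens 1 to 3 from placebo and leaves regimen 4 level with it. With w_P = w_A = 0.40, b = 0.8 and e = 0.4, the difference stays at 1.60 − 1.20 = 0.40, so nothing is masked on that scale.

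**Step 5: what the planned tables can recover.**

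- *Events.* They add up. Total events in an arm minus events under the AD terms gives the non-AD total, mean per subject and rate, provided the SOC/PT table covers the same period as the endpoint.
- *Subjects.* They do not. If *x* subjects have any TEAE and *y* have an AD-worsening TEAE, the number with any non-AD TEAE lies anywhere from x − y to x, because a subject may have both kinds. The same holds for severe, serious and discontinuation-leading events.

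**Step 6: precision.** With 50 per arm, Poisson counts, b = 0.8 and e = 0.4, the non-AD difference has SE = √((1.2 + 0.8)/50) = 0.20. A simple two-sided 5% comparison would then have power of about 0.52; with e = 0.2 it is about 0.18. Arm size limits what can be detected even without AD terms.

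**The case against.** The strongest reply is that nothing is lost. Event totals can be subtracted, as step 5 shows, and all AEs appear in subject listings. Severity, causality, SAE and AESI presentations are planned, and "The number of related AEs and the number of subjects with each type of related AE will be tabulated". A marked excess of non-AD events would show in these. No hypothesis test of the TEAE count is specified, since the hierarchy in Section 11.3.6 covers the primary endpoint only. The safety objective also has a separate measure linked to disease control, time to rescue treatment.

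Most of this stands, so a reader who infers that the plan conceals harm, or that the count cannot be corrected, goes further than the documents allow. What it does not answer is the subject-level summaries. Related AEs depend on the investigator's causality judgement and are a different quantity. A count assembled from listings after unblinding would be post hoc.

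A reader might also infer a contradiction: the same event scored as efficacy failure in one place and as toxicity in another. The text does not support that. In Sections 11.3.7.2 and 11.3.8.1 the intercurrent event is permanent discontinuation because of such an AE, not the AE itself. Section 12.2.1 defines an AE without any claim of causality.

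Finally, the 40% against 20% in Section 11.1 might be read as a measure of the imbalance. It covers withdrawal and intercurrent events for any reason, and persistently severe disease can lead to rescue or withdrawal without a reportable AE. In phase 2a (Section 2.2.2) the most frequent reason for stopping IMP on placebo was withdrawal by subject (7 subjects). Panel 14 assumes that placebo improves on average (−3.5 EASI points at Week 16). A small imbalance is therefore quite possible.

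**Conclusion.** The point holds as a reporting weakness. The sole secondary endpoint and the overall TEAE summary include reportable worsening of AD, and the protocol describes no version without it. If such worsening is more frequent on placebo than on the more effective regimens, mainly 1 to 3, the headline comparison understates any excess of other TEAEs.

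The direction rests on that condition, which is plausible but not documented. The size is unknown, and the ratios in the working are illustrations rather than estimates. The non-AD event total per arm can be worked out from the planned tables; the subject-level figures cannot. The primary analysis and its error control are unaffected. The SAP text that would hold the AD-worsening terms is not in the material reviewed, so it cannot be said that the SAP lacks such a summary, only that the protocol does not call for one. This is a cheap improvement, not a flaw that threatens the trial's conclusions.

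**What to change.** In Section 11.3.13.1, and correspondingly in the SAP before the randomization code is broken:

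- Keep the all-TEAE analysis as planned.
- Add the same per-subject count to Week 16, the event rate per 100 patient-years and the overall TEAE summary (any, severe, serious, leading to discontinuation of IMP), excluding the AD-worsening terms that Section 11.3.7.2 requires the SAP to define.
- Show AD-worsening TEAEs separately by arm.
- State that the safety comparison with placebo will be read from both versions.

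The cost is one more descriptive table, reusing a list the SAP must hold anyway, and a second TEAE figure to interpret. AE collection and clinical management do not change.

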## Panel 4: Objectives, estimands, and endpoints

Objectives	Estimands				Endpoints
	Estimand type	Strategy/ Intercurrent events	Target population	Population level summary	
To compare the efficacy of 4 different dose regimens of LEO 138559 with placebo in subjects with moderate-to-severe AD.	Primary estimand for continuous endpoints	Hypothetical: 
 
- Permanent discontinuation of IMP.
 
- Initiation of rescue treatment.
 
	Subjects with moderate-to-severe AD.	Difference in means of the response variable between the treatment conditions.	
Primary endpoint:
 
 
• Percent change in EASI score from baseline to Week 16.
 
 
Exploratory endpoints:
 
 
• Change in EASI score from baseline to Week 16.
 
• Change in SCORAD score from baseline to Week 16.
 
• Percent change in SCORAD score from baseline to Week 16.
 
• Change in BSA from baseline to Week 16.
 
• Percent change in BSA from baseline to Week 16.
 
• Change in DLQI (and individual domain scores) from baseline to Week 16.
 
• Percent change in DLQI (and individual domain scores) from baseline to Week 16.
 
• Change in POEM score (and individual item scores related to itch and sleep) from baseline to Week 16.
 
• Percent change in POEM score from baseline to Week 16.
 
• Change in EQ-5D-5L index score from baseline to Week 16.
 
• Percent change in EQ-5D-5L index score from baseline to Week 16.
 
• Change in EQ-5D-5L VAS score from baseline to Week 16.
 

Objectives	Estimands				Endpoints
	Estimand type	Strategy/ Intercurrent events	Target population	Population level summary	
					
 
Percent change in EQ-5D-5L VAS score from baseline to Week 16.
 
Change in HADS score from baseline to Week 16.
 
Percent change in HADS score from baseline to Week 16.
 
Change in Difficulty [REDACTED] (weekly average) from baseline to Week 16.
 
Percent change in Difficulty [REDACTED] (weekly average) from baseline to Week 16.
 
Change in Nocturnal [REDACTED] (weekly average) from baseline to Week 16.
 
Percent change in Nocturnal [REDACTED] (weekly average) from baseline to Week 16.
 
Change in Frequency of [REDACTED] During the Night (weekly average) from baseline to Week 16.
 
Percent change in Frequency of [REDACTED] During the Night (weekly average) from baseline to Week 16.
 
Change in WPAI-SHP domain from baseline to Week 16.
 
Percent change in WPAI-SHP domain from baseline to Week 16.
 
Change in SCORAD Part C (Pruritus VAS) score from baseline to Week 16.
 
Percent change in SCORAD Part C (Pruritus VAS) score from baseline to Week 16.
 

Objectives	Estimands				Endpoints
	Estimand type	Strategy/ Intercurrent events	Target population	Population level summary	
	Suppl. estimands for continuous endpoints	Hypothetical supplementary: 
 
- Permanent discontinuation of IMP.
 
- Initiation of rescue treatment.
 
			
Primary endpoint:
 
 
• Percent change in EASI score from baseline to Week 16.
 
 
Exploratory endpoints:
 
 
• Change in EASI score from baseline to Week 16.
 
• Change in SCORAD score from baseline to Week 16.
 
• Percent change in SCORAD score from baseline to Week 16.
 
• Change in BSA from baseline to Week 16.
 
• Percent change in BSA from baseline to Week 16.
 
• Change in DLQI (and individual domain scores) from baseline to Week 16.
 
• Percent change in DLQI (and individual domain scores) from baseline to Week 16.
 
• Change in POEM score (and individual item scores related to itch and sleep) from baseline to Week 16.
 
• Percent change in POEM score from baseline to Week 16.
 
• Change in EQ-5D-5L index score from baseline to Week 16.
 
• Percent change in EQ-5D-5L index score from baseline to Week 16.
 
• Change in EQ-5D-5L VAS score from baseline to Week 16.
 
• Percent change in EQ-5D-5L VAS score from baseline to Week 16.
 

Objectives	Estimands				Endpoints
	Estimand type	Strategy/ Intercurrent events	Target population	Population level summary	
					
 
• Change in HADS score from baseline to Week 16.
 
• Percent change in HADS score from baseline to Week 16.
 
• Change in Difficulty [REDACTED] (weekly average) from baseline to Week 16.
 
• Percent change in Difficulty [REDACTED] (weekly average) from baseline to Week 16.
 
• Change in Nocturnal [REDACTED] (weekly average) from baseline to Week 16.
 
• Percent change in Nocturnal [REDACTED] (weekly average) from baseline to Week 16.
 
• Change in Frequency of [REDACTED] During the Night (weekly average) from baseline to Week 16.
 
• Percent change in Frequency of [REDACTED] During the Night (weekly average) from baseline to Week 16.
 
• Change in WPAI-SHP domain from baseline to Week 16.
 
• Percent change in WPAI-SHP domain from baseline to Week 16.
 
• Change in SCORAD Part C (Pruritus VAS) score from baseline to Week 16.
 
• Percent change in SCORAD Part C (Pruritus VAS) score from baseline to Week 16.
 
 
Treatment policy: - Permanent discontinuation of IMP.
 
Primary endpoint: Percent change in EASI score from baseline to Week 16.

Objectives	Estimands				Endpoints
	Estimand type	Strategy/ Intercurrent events	Target population	Population level summary	
		- Initiation of rescue treatment.			
	Primary estimand for binary endpoints	Composite: 
 
- Permanent discontinuation of IMP due to lack of efficacy or an AE related to worsening of AD.
 
- Initiation of rescue treatment.
 
 Hypothetical: 
 
- Permanent discontinuation of IMP due to reasons other than lack of efficacy or an AE related to worsening of AD.
 
	Subjects with moderate-to-severe AD.  Subjects with moderate-to-severe AD, having an average ADSD Worst █ score of $\geq 4$ at baseline.  Subjects with moderate-to-severe AD, having a DLQI score of $\geq 4$ at baseline.  Subjects with moderate-to-severe AD, having a POEM	Difference in response rates of the response variable between the treatment conditions.	Exploratory endpoints: 
 
• Achievement of EASI-50 at Week 16.
 
• Achievement of EASI-75 at Week 16.
 
• Achievement of EASI-90 at Week 16.
 
• Achievement of EASI-100 at Week 16.
 
• Achievement vIGA-AD score of 0 (clear) or 1 (almost clear) at Week 16.
 
• Reduction of ADSD Worst █ score (weekly average) <math>\geq 4</math> from baseline to Week 16.
 
 Exploratory endpoint: 
 
• Reduction of ADSD Worst █ score (weekly average) <math>\geq 4</math> from baseline to Week 16.
 
 Exploratory endpoint: 
 
• Reduction of DLQI <math>\geq 4</math> from baseline to Week 16.
 
 Exploratory endpoint: 
 
• Reduction of POEM <math>\geq 4</math> from baseline to Week 16.
 

Objectives	Estimands				Endpoints
	Estimand type	Strategy/ Intercurrent events	Target population	Population level summary	
			score of $\geq 4$ at baseline.		Exploratory endpoints: 
 
• Achievement of EASI-50 at Week 16.
 
• Achievement of EASI-75 at to Week 16.
 
• Achievement of EASI-90 at Week 16.
 
• Achievement of EASI-100 at Week 16.
 
• Achievement vIGA-AD score of 0 (clear) or 1 (almost clear) at Week 16.
 
• Reduction of ADSD Worst █ score (weekly average) <math>\geq 4</math> from baseline to Week 16.
 

	Suppl. estimand for binary endpoints	Treatment-policy: 
 
- Permanent discontinuation of IMP.
 
- Initiation of rescue treatment.
 
	Subjects with moderate-to-severe AD.		
To compare the safety of 4 different dose regimens of LEO 138559 with placebo in subjects with moderate-to-severe AD.	Primary estimand for time-to-event endpoints	While on treatment: 
 
- Permanent discontinuation of IMP.
 
	Subjects with moderate-to-severe AD.	Difference in the cumulative incidence at Week 16.	Exploratory endpoint: 
 
• Time from baseline to use of any rescue treatment.
 

	Suppl. estimand for time-to-event endpoints	Composite: 
 
- Permanent discontinuation of IMP.
 
	Subjects with moderate-to-severe AD.	Difference in the cumulative incidence at Week 16.	Exploratory endpoint: 
 
• Time from baseline to use of any rescue treatment.
 

**Abbreviations:** AD = atopic dermatitis; AE = adverse events; ADSD = Atopic Dermatitis Symptom Diary; DLQI = Dermatology Life Quality Index; EASI = Eczema Area and Severity Index; EASI-50 = at least 50% decrease in EASI score; EASI-75 = at least 75% decrease in EASI score; EASI-90 = at least 90% decrease in EASI score; EASI-100 = at least 100% decrease in EASI score; EQ-5D-5L = EuroQoL 5 Dimension Health Questionnaire 5 Level; HADS = Hospital Anxiety and Depression Scale; IMP = investigational medicinal product; POEM = Patient-Oriented Eczema Measure; Suppl. = supplementary; VAS = Visual Analogue Scale; vIGA-AD = Validated Investigator Global Assessment Scale for Atopic Dermatitis; WPAI-SHP = Work Productivity and Activity Impairment: Specific Health Problem.

THIS DOCUMENT CONTAINS CONFIDENTIAL INFORMATION AND MUST NOT BE COPIED OR MADE AVAILABLE TO ANY THIRD PARTY WITHOUT THE PRIOR WRITTEN CONSENT OF THE LEO PHARMA GROUP

TMF-000757181 - Version 5.0

